11.2 Study-specific considerations and risks

The study assumes that a further reduction in postoperative pain and rescue-opioid consumption after TKA is possible with postoperative cryoneurolysis compared to a sham block. This could secure a better postoperative convalescence and rehabilitation as well as lower the risk of complications.

Cryoneurolysis has been used to treat acute pain following herniorrhaphy [13], tonsillectomy [14], and thoracotomy [15] via the surgical incision. Recently, cryoneurolysis has been used for the treatment of knee pain. In May 2019, the United States Department of Health and Human Services published a report recommending the use of cryoanalgesia as a treatment option for knee pain due to osteoarthritis [33]. At Hvidovre Hospital cryoneurolysis is offered to selected patients with chronic post-herniorrhaphy pain. However, it is not part of standard care for acute post-TKA pain but the anesthetist performing the procedure is well trained.

Patients will receive cryoneurolysis of the ISN and ACFN nerves or a sham block at the same locations. The procedure will be performed with conscious patients after the injection of local anesthesia. The patient may experience tingling and slight pain in the area, but the procedure may be stopped at any time should the patient wish to. The control group will receive a sham-block using only local anesthesia and the insertion guide of the cryoprobe without freezing. The cryoprobe will be held close by for blinding purpose.

Generally, side effects following cryoneurolysis are mild and self-limiting [18]. Some patients experience mild to moderate pain involved in the initial application (first freeze sequence), but this usually resolves within 30 s. The most commonly reported side effects are bruising, numbness, redness, tenderness upon palpation, and swelling [20]. Due to the risk of

bleeding, patients with anticoagulation therapy without adequate pause or bleeding disorders are excluded. If the ice ball involves the skin, risks may include frostbite, alopecia, depigmentation and/or hyperpigmentation. Infection appears to be extremely rare [28]. Damage to the surrounding tissue may occur if the probe is moved before adequate thaw period, as the tissues can adhere to the probe. This may theoretically cause permanent nerve damage. However, there are no published reports of permanent nerve damage or neuroma formation [34]. There are reports of patients experiencing severe dysesthesia interfering with sleep and daily activities. This has been observed between 2-14 days after the treatment. In one study severe dysesthesia occurred in 2 out of 169 patients (1.2%) treated for postoperative pain after TKA [20]. Another retrospective study on 50 patients receiving cryoanalgesia for postoperative pain after TKA found no significant side effects in the treated group [19]. In a study on post-herniorrhaphy pain, no patients experience allodynia but three out of 24 patients experienced some degree of hyperalgesia following cryoanalgesia [13]. It is noteworthy that two randomized controlled trials reported a significantly higher incidence of neuropathic pain for subjects treated with cryoneurolysis at 8 weeks [35] and 6 months after open thoracotomy [36]. These results are in contrast with studies of post-TKA pain and the reason for this discrepancy remains unknown but may be due to the double crush hypothesis given the high incidence of surgical procedure-related nerve injury during open thoracotomy [34].

Due to the long-lasting effects that cryoneurolysis may have, we study the subjects for up to 6 months after cryoneurolysis.

The study will not bring other changes to the patient's course of treatment in relation to the preoperative preparation, level of information, type of anesthesia, surgical procedure, postoperative care, physiotherapy, and discharge, the exceptions being cryoanalgesia for patients with high levels of postoperative pain. All these other steps will be following our fast-track program.

Participating patients help investigate the effect of cryoanalgesia as a potential new treatment for patients with moderate to severe pain after TKA surgery, which can potentially reduce the length of stay, the rate of postoperative complications, and the intake of opioids. This could potentially change the course of treatment and postoperative convalescence for thousands of TKA patients worldwide and lead to changes in national and international clinical guidelines.

Patients participating in the study are not secured a gain by participating in the study, but do not receive inferior treatment compared to patients outside the study.

12 Side effects

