4.1 Intervention groups

Patients eligible for participating in the study will be evaluated 24 h after surgery for the presence of moderate to severe pain. Patients with pain (VAS 0-100 mm) ≥ 45 during a 5 m walk test are included.

The study will include the following intervention groups:

Sham cryo (sham-group): Postoperative sham cryoneurolysis of the lower extremity.

Cryoneurolysis (cryo-group): Postoperative cryoneurolysis of the superficial genicular nerves, i.e., the infrapatellar branches of the saphenous nerve (ISN) and the anterior femoral cutaneous nerve (AFCN).

Both cryoneurolysis and the sham block will be performed using ultrasound and a nerve stimulator (*see 8.2 Intervention page 11*). An injection of ropivacaine around the nerves will be administered in both groups preceding the intervention. The patient will be blinded but the anesthetist performing the intervention will be unblinded.

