5.1 Inclusion criteria

- Age ≥ 18
- Primary unilateral TKA
- Ability to participate in the study (understand written and spoken Danish language, self-reported pain and satisfaction)
- Signed written informed consent form
- Pain (VAS 0-100 mm) ≥ 45 during a 5-meter walk test at 24 h (20-28h) postoperatively

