5.2 Exclusion criteria

- Ongoing treatment of systemic glucocorticoids or other immunosuppressant treatment apart from inhaled steroids
- Insulin-dependent diabetes
- Pregnancy or breastfeeding*
- Mental disability that could impair a patient's decision-making capability of giving informed consent and not enabling valid data collection.
- Patients with known diagnoses of schizophrenia, ongoing psychosis, bipolar disease and/or a history of ongoing anti-psychotic treatment.
- Patients with modulated pain-reception (experience) based on other diseases or injuries, e.g. spinal cord or brain injury, severe polyneuropathies or neurologic disorders.
- Posttraumatic osteoarthritis as reason for TKA
- Bleeding disorder
- Localized infection in the treatment area

- Cryoglobulinemia, cold urticaria, paroxysmal cold haemoglobinuria, or Raynaud's syndrome
- Perioperative peripheral nerve block

*Pregnancy: No women with suspected or proven pregnancy are eligible for inclusion. The following will be considered as safe contraception: intrauterine device or hormonal contraception. For women aged between 18-50 years, a urine HCG test for pregnancy will be performed.

6. Randomization and blinding

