8.2 Intervention

The intervention will take place after the inclusion at 20-32 h after TKA surgery. The procedure will be performed at the Dept. of Anesthesiology.

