13.1 Recruitment

Patients planned for TKA are screened in accordance with the inclusion and exclusion criteria and informed at the pre-surgery examination or anesthetist appointment or via phone before the surgery. Patients receive written information about the study before the surgery date and is told to consider their possible participation. If the patient declines all contact to the research personnel, the investigator is informed. If not, the patient is contacted for further information.

Patients who are found fit to participate is given adequate oral information about the study purpose, setting, advantages and risks.

An electronic screening log is kept tracking declining patients and later to fulfill the Consort diagram. This log does not contain names or other person-specific information, which would allow for future identification. The screening log is kept for later examination of the study cohort, and reasons for declining participation. No study related data is part of the screening log.

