13.2 Informed consent

The information will be given without disturbance and interruptions and the patient is informed that he/she can schedule a new information interview and to bring a bystander/relative if wished. The information interview will be postponed until the bystander is present if requested. The information interview can be by attendance at the facility or by phone.

The patient receives the written information for participants at the pre-surgery appointment or if needed by secure email. The patient is informed that he/she is entitled to at least one day of reflection/consideration. If the patient does not want to participate, they can do so without informing about the reason for this.

The investigator or research-nurse informs the patient and collect the signed consent form. When needed, in case of sickness or holiday, other research collaborators can collect the signed consent form. The signed consent will be done before the surgery. Both the hospital and the patient will have a signed Consent form. The applicable guidelines and restrictions concerning informed consent brought by the National Ethics Committee is attached to the patient-information. Information for the participant and the Consent form is attached as Appendices 2 and 3.

The patient will be informed that participation is voluntary, and that withdrawal can happen anytime without justification, also after the signed consent, without this affecting their further treatment course and stay at the facility. They will also be informed that the investigator can pull them out of the study anytime at their discretion.

14. Information from the electronic patient journal

All information from the EPJ will be obtained after signing the informed consent form the day after surgery. The consent gives the primary investigator, the sponsor, and sponsor's representatives direct access to gather information from the patient's journal including the EPJ. The information obtained is necessary for the completion of the study and to make sure that the study is carried out correctly, which includes self-control and quality control. After the informed consent, the following information will be obtained from the patient's EPJ:

- Gender
- Age
- Height
- Weight
- Co-morbidities
- American Society of Anesthesiologist (ASA) score

- Pain Catastrophizing Scale (PCS)
- Current medical prescriptions (including glucocorticoids, immunosuppressants, opioids, insulin, and anti-psychotics)

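### The risk section excludes patients on anticoagulation without adequate pause, but the exclusion list in section 5.2 has no such item

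*Combined protocol and SAP*

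**What the plan says.** Section 11.2, in its account of the side effects of cryoneurolysis, gives bleeding risk as the reason that "patients with anticoagulation therapy without adequate pause or bleeding disorders are excluded". This is a statement of fact about who is eligible, and it covers two groups.

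Section 5.2 lists 11 exclusions. One concerns bleeding: "Bleeding disorder". Anticoagulant treatment is not mentioned.

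Section 13.1 says that patients planned for surgery are "screened in accordance with the inclusion and exclusion criteria". Final inclusion comes after the operation. Section 4.1 states: "Patients eligible for participating in the study will be evaluated 24 h after surgery for the presence of moderate to severe pain". Section 5.1 sets the pain threshold "during a 5-meter walk test at 24 h (20-28h) postoperatively", and section 8.2 adds: "The intervention will take place after the inclusion at 20-32 h after TKA surgery".

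Section 14 lists what is taken from the patient record after consent, including "Current medical prescriptions (including glucocorticoids, immunosuppressants, opioids, insulin, and anti-psychotics". On timing it says: "All information from the EPJ will be obtained after signing the informed consent form the day after surgery".

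**The concern.** The protocol relies on an exclusion in its risk discussion that is missing from the list of criteria. Half of the 11.2 rule reached section 5.2 and the other half did not. Staff who work from section 5 would have no prompt to ask about anticoagulants and could include a patient whom the protocol elsewhere says is excluded.

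What is at stake is mainly patient safety. Both arms have an invasive procedure: the sham arm receives the local anaesthetic injection and the insertion guide, without the freezing. A committee or authority reading 11.2 would also take it that the safeguard is in force.

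There is a small effect on the analysis sets. Section 7.2 defines the per-protocol population by the absence of major deviations, and section 17.3 allows withdrawal for significant violations. Including a patient on unpaused anticoagulation would breach 11.2 but not 5.2, so the documents do not settle how that patient would be classed.

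**Working it through.** No figure in the plan bears on this point, so the check is a comparison of texts.

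**1. The two statements side by side.**

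| Group | Section 11.2 | Section 5.2 |
|---|---|---|
| Bleeding disorder | Excluded | Listed (1 of 11 items) |
| Anticoagulation without adequate pause | Excluded | Not listed (0 of 11 items) |

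**2. Could the listed item cover both groups?** Not on the protocol's own wording. Section 11.2 names the two groups separately, joined by *or*, so it treats treatment with an anticoagulant as distinct from a bleeding disorder.

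**3. Is the rule stated anywhere else?** Anticoagulation appears once in the supplied text, in the 11.2 sentence. Sections 4.1, 5.1, 5.2, 8.2, 13.1 and 14 do not mention it.

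**4. Does the postoperative inclusion step pick it up?** Sections 4.1 and 5.1 describe only the pain assessment at that step. Section 8.2 places the procedure after inclusion, at 20-32 h. None of them describes a check of anticoagulant treatment.

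**5. Does the record review pick it up?** Section 14 names five drug classes. Four correspond to a 5.2 exclusion (glucocorticoids, immunosuppressants, insulin, anti-psychotics), one does not (opioids), and none is an anticoagulant: 4 + 1 + 0 = 5. The list is introduced as examples, so anticoagulants may well be recorded under current prescriptions. But nothing in section 14 links such a record to an eligibility decision.

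**6. Is the pause defined?** No. The 11.2 sentence sits among the risks of cryoneurolysis, which suggests that the study procedure is the reference point, but the text does not say so. The surgery and the study procedure are 20-32 h apart, so the choice could change who meets the rule.

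**7. Does it touch the design figures?** No. The sample size in section 7.1 rests on a mean of 390, an SD of 208, a 50% reduction (0.5 × 390 = 195), a two-sided 0.05 level and 80% power. None of these depends on the anticoagulation rule.

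**The case against.** The strongest reply is that this is an omission and not a contradiction. Nothing in 5.2 permits unpaused anticoagulation, 11.2 is part of the same protocol and speaks plainly, and a reader of the whole document would know that the exclusion applies. That is true, and it is why the gap is narrow. It does not make the list complete: 5.2 is where a reader looks for the exclusions, and it leaves out one that the protocol says is in force.

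Second, section 13.1 refers to the criteria without citing section 5, and it is conjecture that staff would use that section alone. The inference is nevertheless the natural one, since section 5 is headed as the selection criteria and 11.2 falls under ethical considerations.

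Third, section 14 is a data-collection list. It does not claim to drive eligibility for any drug, and its examples are not exhaustive. This is fair: section 14 shows only that no second written check exists. Its timing is also unsettled, because 13.2 places the signed consent before surgery while sections 8 and 14 place it on the day after. The finding does not depend on which is right.

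Fourth, the appendices are supplied by title only and some front matter was removed, so the rule may be repeated in the study plan or the protocol summary. That cannot be checked. Even if it is repeated there, 5.2 and 11.2 would still differ.

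**Conclusion.** The concern holds. Section 5.2 as written is incomplete against section 11.2: it would admit a patient on anticoagulation without adequate pause, whom 11.2 says is excluded. This should be fixed, because it is a safety exclusion with a stated reason and it bears on an invasive procedure in both arms.

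No numerical size can be given, since the documents report neither how many of these patients take anticoagulants nor how pauses are handled. Confidence is high on the discrepancy between the two sections. Whether the exclusion would be missed in practice is less certain: that assumes staff screen from section 5, and that no removed or unsupplied text restates the rule.

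**What to change.** Reconcile 5.2 and 11.2 so that both carry the same anticoagulation rule. The responsible clinicians should decide what that rule is; this review takes no position on it or on what counts as an adequate pause. The text should say whether any pause is judged relative to the surgery or to the study procedure.

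If the exclusion is kept, name anticoagulants in the section 14 prescription list and add a check at the postoperative inclusion step. If it is not kept, correct the statement in 11.2.

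The drafting cost is about one line in 5.2 or 11.2, and one word in section 14 if the exclusion stays. Keeping it may produce a few more screen failures. Section 11.1 requires the authorities to be told of substantial or essential protocol changes, so the sponsor should judge whether this edit qualifies.

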12.1 Intervention specific side effects

Possible side effects of cryoneurolysis are discussed above (see 11.2 *Study-specific considerations and risks*). These may include [18]:

- Altered sensation
- Bruising
- Crusting
- Hyperpigmentation

- Itching
- Local pain
- Numbness
- Redness
- Swelling
- Tenderness
- Tingling
- Aggravated pain
- Loss of motor function outside the treatment area
- Infection

12.2 Definitions

Adverse Events (AE) are defined as any unwanted event in a patient or in a study subject in a clinical study after treatment with a drug, without necessarily having any connection to the treatment and the adverse event.

Adverse Reactions (AR) are defined as any harmful and unwanted reaction related to the intervention drug regardless of the dose.

Serious Adverse Events (SAE) are defined as any adverse event, regardless of dose of study-drug, resulting in death, a life-threatening condition (according to the investigator's assessment, the patient was in an immediate risk of dying from the SAE, when it occurred), any event leading to hospitalization or prolonged stay (>2 days after index surgery), significant or persistent disability or incapacity or results in a congenital anomaly or birth defect.

Serious Adverse Reactions (SAR) are defined as any adverse reaction resulting in death, a life-threatening condition (according to the investigator's assessment, the patient was in an immediate risk of dying from the SAE, when it occurred), any event leading to hospitalization or prolonged stay (>2 days after index surgery), significant or persistent disability or incapacity or results in a congenital anomaly or birth defect.

Suspected Unexpected Serious Adverse Reactions (SUSAR) are defined as any suspected adverse reaction which is both serious and unexpected (not consistent with information available to date). The summary of product characteristics for dexamethasone (see link on bottom of page 15) will be used as reference to evaluate if the serious adverse reaction is expected or unexpected.

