8.1.2 Anesthesia

All included patients will receive general anesthesia or a neuraxial blockade in the form of a spinal anesthesia administered at level L2-L4, by injecting 2-3 ml of hyperbaric bupivacaine 0.5%. If spinal anesthesia is performed, perioperative sedation with propofol or other sedatives is optional and done in agreement with the patient. According to local guidelines, dexamethasone 0.3 mg/kg or 1 mg/kg IV rounded up to nearest 10 mg will be administered prior to surgery to patients with a pain catastrophizing scale score ≤ 20 or > 20 , respectively [27]. A supplement of local infiltration analgesia is administered directly into the surrounding tissue of the knee at the end of surgery, according to local operating procedure.

Tranexamic acid is administered as 1 g preoperatively, 1 g 3 h postoperatively, and 1 g in the surgical ward according to local operating procedure to prevent bleeding.

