9.1 Ropivacaine

The cryoneurolysis intervention itself does not involve any study drugs. However, ropivacaine 5 mg/ml will be administered preceding the cryoneurolysis or the sham block. The ropivacaine is contained in plastic ampules.

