12.3 Reporting of side effects

As we are testing a relatively new procedure, all AEs will be reported at every follow-up.

All AEs will be assessed by the investigators and sponsor for association with the study drug and possible causality and reported according to present law. The severity of the AE and the possible association to the study drug will be evaluated according to following guidelines by investigators and sponsor:

1. **Not related** – No temporal association, other reasons/etiologies most likely cause of AE
2. **Possibly related** – Lesser clear association, other reasons/etiologies could be cause of AE.

3. **Likely related** – Clear temporal association with improvement in discontinuation of study drug, and not reasonably explained by the clinical condition of the patient.
4. **Related** – Clear temporal association with treatment or clinical assessment.

Patients experiencing AEs will be monitored with relevant clinical assessments and laboratory tests at the discretion of the attending and treating physician. All AEs will be followed until satisfactory restitution or stabilizing of the patient. Time of origin and ending, level of severity and consequences for the patient and study will be reported.

A Serious Adverse Event (SAE) is not dose-dependent and results in a significant risk of death or disability for the participant, including, but not limiting itself, to an event that:

1. causes death.
2. is life-threatening - the participant was at imminent risk of dying from the adverse event, according to the investigator's assessment.
3. requires hospitalization or prolongs already occurring hospitalization.
4. causes permanent disability.

All SAEs must be reported by investigators to sponsor within 24 hours from time of discovery.

Investigators are responsible for the registration, monitoring and reporting of all AEs and SAEs in the patient CRF and in the specific Trial Master File. Sponsor is responsible for the ongoing surveillance of the risk/benefit ratio in the study. If situations with risk or danger for the patient's safety or the execution of the study should occur, this must always and immediately be reported to the Danish Medicines Agency. Reporting of such situations or risks must also be done to all involved investigators and the approving ethics committee.

A safety report including all SAE and SAR must be made once a year and reported to the Danish Medicines Agency and the approving Ethics committee.

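### Wrong as written (safety reporting): section 12.2 judges whether a serious adverse reaction is expected against the dexamethasone product summary, although dexamethasone is background care and the trial tests cryoneurolysis against sham

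*Combined protocol and SAP*

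**What the plan says.** Section 12.2 defines a SUSAR as a suspected adverse reaction that is "both serious and unexpected (not consistent with information available to date". The next sentence names the document that settles expectedness: "The summary of product characteristics for dexamethasone (see link on bottom of page 15) will be used as reference". An adverse reaction, the term on which SAR and SUSAR build, is "any harmful and unwanted reaction related to the intervention drug regardless of the dose".

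Section 12.3 sets the causality assessment: "All AEs will be assessed by the investigators and sponsor for association with the study drug and possible causality". It opens with a wider statement: "As we are testing a relatively new procedure, all AEs will be reported at every follow-up". It ends with the SUSAR rule, under which the sponsor has 7 days to report to the medicines agency, the ethics committee and all investigators.

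On the treatments themselves, section 8.1.2 says: "According to local guidelines, dexamethasone 0.3 mg/kg or 1 mg/kg IV rounded up to nearest 10 mg will be administered prior to surgery". Section 9.1 says: "The cryoneurolysis intervention itself does not involve any study drugs". Section 4.1 says: "An injection of ropivacaine around the nerves will be administered in both groups preceding the intervention".

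**The concern.** Expectedness is the last step in deciding whether a serious reaction goes to the authorities within 7 days. It works only if the reference describes the known effects of what is being studied. Here the reference describes a different product, given to patients before they could be found eligible. Neither cryoneurolysis nor ropivacaine has a named reference.

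Two assessors could therefore classify the same serious event differently. One might use the general test of what is known to date, and the other the named product summary. This matters more than usual because section 12.3 itself calls the procedure relatively new.

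**Working it through.** The plan gives no figure for this point and no formula applies. The check sets the relevant sections side by side.

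1. **Role of dexamethasone.** Section 8.1 places all perioperative care under local procedures. Section 8.1.2 gives dexamethasone before surgery, at a dose that depends on the pain catastrophizing score (20 or below, or above 20). Eligibility is judged at 24 h after surgery, with a window of 20-28 h (section 5.1), and the intervention follows at 20-32 h (section 8.2). Dexamethasone has thus been given before eligibility is known and cannot depend on allocation.

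2. **Section 9.** Section 9.1 covers ropivacaine. Section 9.2 lists possible rescue drugs: adrenaline, atropine, intralipid, midazolam and ondansetron. Dexamethasone appears in neither.

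3. **What is tested.** Under sections 4.1 and 8.2.2 the arms differ only in whether the nerves are frozen. Ropivacaine is common to both. By section 9.1, freezing involves no study drug.

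4. **Whether another section supplies a reference.** Section 12.1 lists possible side effects of cryoneurolysis. Section 11.2 describes its risks, including severe dysesthesia in 2 of 169 patients in one cited study. Neither section is named as the expectedness reference, and nothing elsewhere overrides the dexamethasone sentence.

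5. **The two tests in section 12.2.** Take a serious case of an effect described in section 11.2. Under the general test it is already known. Under the named reference the answer depends on whether the dexamethasone summary lists it. That summary is not in the documents, so the answer cannot be given here.

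6. **Following an event through the definitions.**
   - If drug is read broadly, to include the procedure, a serious reaction to freezing is an adverse reaction and its expectedness is judged against dexamethasone.
   - If drug is read narrowly, only a reaction to ropivacaine qualifies, and that too is judged against dexamethasone.
   - The reference is therefore wrong on both readings. The choice of reading changes only which events reach it.

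7. **What does not pass through this step.** The adverse-event definition asks for prior treatment with a drug, and ropivacaine meets that in both arms. Adverse-event capture at follow-up, reporting of serious events to the sponsor within 24 hours, immediate reporting of risks, and serious events in the yearly and final reports need neither the reference nor the adverse-reaction label.

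8. **Scale.** The documents give no rate of serious reactions to cryoneurolysis. As an illustration for one effect only, applying 2/169 to the 22 cryo patients gives 22 × 2/169 = 0.26 expected cases of severe dysesthesia, and a chance of at least one case of 1 − (167/169)^22 = 0.23. Severe is not the same as serious in the reporting sense, so this does not count misclassified events. It only suggests that few would be involved.

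**The case against.** The strongest reply is that the defect is narrow and that the drug wording is merely loose. Much of this stands.

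- **Drug wording.** A reader might infer that a serious harm from freezing is not an adverse reaction at all and so escapes SAR and SUSAR handling. The documents do not support that as the natural reading. Section 17.2 uses study drug and study intervention in parallel. The highest causality grade in section 12.3 refers to treatment, not drug. Section 12.1, directly before the definitions, is about cryoneurolysis alone, and section 12.3 opens by referring to a procedure. What remains is that the adverse-reaction and causality sentences do not expressly name the procedure, which calls for clarification.

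- **Lost reports.** A reader might infer that serious events would drop out of the yearly report. They would not: that report covers all serious adverse events as well as SARs, so only the label could change.

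- **Direction of error.** A reader might infer systematic over-reporting or under-reporting. Either would need the content of the dexamethasone summary, which is not available here.

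- **Other wording in section 12.** The grade that refers to improvement on discontinuation fits poorly with a completed single procedure, but no text ties SAR or SUSAR status to that grade. The prolonged-stay criterion is worded differently in sections 12.2 and 12.3, but that is a separate matter. Neither adds to this point.

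The reply does not reach the dexamethasone sentence itself. The page-15 link is not visible in the text available for review, but the sentence is complete without it, and no section repairs it.

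**Conclusion.** The point holds, in limited form, and should be fixed. The named expectedness reference is wrong: it belongs to a background drug that is neither randomised nor listed in section 9. It also sits uneasily with the general test in the sentence before it. The consequence is confined to the expectedness decision and hence to the 7-day SUSAR report. The drug wording is a lesser ambiguity, and the protocol's own text favours the broad reading.

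No number of misclassified events can be stated, and the direction of any misclassification is unknown. The conclusion that the reference does not fit rests on the protocol text alone and needs no assumption about what the dexamethasone summary contains. The other safety safeguards and the efficacy analysis are not affected.

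**What to change.** Amend section 12 as follows.

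- Delete the dexamethasone reference from section 12.2.
- Name an expectedness reference that fits what is studied: the cryoneurolysis procedure, for which the information in sections 11.2 and 12.1 is a starting point, and ropivacaine as the drug given in both arms. Make it agree with the general test in the SUSAR definition.
- In sections 12.2 and 12.3, replace intervention drug and study drug with study intervention, defined as the cryoneurolysis or sham procedure together with ropivacaine.

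The cost is a wording amendment, for which the sponsor must choose the reference. It needs no new data, visits or patients.
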